**Appendix 2.10 van der Heijde modified Total Sharp Score (mTSS)**

The mTSS is a detailed scoring method evaluating erosions, joint space narrowing, (sub)luxation, ankylosis, gross osteolysis, and pencil in cup phenomena.

Hands/wrists radiographs will be obtained by sites and sent for central review. The central reviewers will use the modified total Sharp Score (mTSS) to evaluate for radiographic damage and progression.

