1.3. Schedule of Activities

Procedure	Screening (\leq 28 days before Day 1)	Day 1 / W0	Study Week (\pm 3 days) ^a													EOT ^b (\pm 3 days)	Safety FU ^b (\pm 5 days)	PK & ADA FU/ End of Study ^b (\pm 5 days)
			1	2	3	4	8	12	16 ^c	17	18	20 ^c	24 ^c	32 ^c	36	40		
Informed consent	X																	
Inclusion and exclusion criteria	X	X																
Demography	X																	
Physical examination	X																X	
Weight	X	X															X	X
Height	X																	
Medical and medication history	X	X																
Alcohol and nicotine use	X																	
Vital signs ^d	X	X	X	X	X	X	X	X	X	X	X	X	X	X	X	X	X	X
12-lead ECG ^e	X								X								X	X
Chest x-ray ^f	X																	

Procedure	Screening (≤ 28 days before Day 1)	Day 1 / W0	Study Week (± 3 days) ^a													EOT ^b (±3 days)	Safety FU ^b (±5 days)	PK & ADA FU/ End of Study ^b (±5 days)
			1	2	3	4	8	12	16 ^c	17	18	20 ^c	24 ^c	32 ^c	36	40		
HADS		X							X								X	
AE reporting ^g		X															→	
SAE reporting ^g	X																→	X
Concomitant medication		X															→	X
Efficacy Assessments																		
Subject's Global Impression of Change									X								X	
Subject's Global Assessment of Disease Activity		X		X		X		X			X	X	X	X	X		X	
Subject's Assessment of Pain (VAS)		X		X		X		X			X	X	X	X	X		X	
Subject's Assessment of Spinal Pain (NRS)		X							X			X					X	
Widespread Pain Index		X																
HAQ-DI		X		X		X		X	X				X	X	X		X	
PsAID-9		X		X		X		X	X				X	X	X		X	
SF-36		X						X	X				X	X			X	
FACIT-F		X							X				X				X	
Joint Assessments ^h	X	X	X	X	X	X					X	X	X	X	X		X	
Investigator's Global Assessment of Disease Activity		X		X		X		X	X			X	X	X	X		X	
PASI/affected BSA		X		X		X		X	X			X	X				X	
mNAPSI		X						X	X			X	X				X	

Procedure	Screening (≤ 28 days before Day 1)	Day 1 / W0	Study Week (± 3 days) ^a													EOT ^b (±3 days)	Safety FU ^b (±5 days)	PK & ADA FU/ End of Study ^b (±5 days)
			1	2	3	4	8	12	16 ^c	17	18	20 ^c	24 ^c	32 ^c	36	40		
Leeds Enthesitis Index		X				X		X	X				X	X	X		X	
SPARCC Enthesitis Index		X				X		X	X				X	X	X		X	
Leeds Dactylitis Index		X				X		X	X				X	X	X		X	
Investigator Question on Presence of Axial Involvement		X																
Radiographs for PsA (x-ray) – Hands, Wrists, and Feet		X								X ⁱ							X ⁱ	
Radiograph - Pelvis		X																
Laboratory Assessments																		
Serology (HBV ^j , HCV, HIV)	X																	
TB test ^k	X																	
Hematology/ Chemistry	X	X				X	X	X	X				X	X	X	X	X	X

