8.1.3.8. Radiographic Assessment and modified total Sharp score

Radiographs of hands, wrists, and feet will be performed at baseline, Week 16, and Week 52 or EOT in order to evaluate the presence and extent of PsA-related structural damage over the course of the study. Radiograph of the pelvis will be performed at baseline.

Radiographs of hands, wrists, and feet will be performed if subjects discontinue the study drug after Week 16 and it has been at least 12 weeks from the date of last radiographs obtained.

Radiographs should be obtained as close as possible to the last dose of study drug.

Psoriatic arthritis radiographic progression will be measured by the modified total Sharp score (mTSS). The mTSS is a detailed scoring method evaluating erosions, joint space narrowing, (sub)luxation, ankylosis, gross osteolysis, and pencil in cup phenomena. It typically assesses joints of the hands and feet, including the second to fifth distal interphalangeal joints of both hands ([van der Heijde et al, 2005](#)).

The maximum score for erosions is 5 in the joints of the hands and 10 in the joints of the feet. Scores for erosions are as follows: 0 = no erosions; 1 = discrete erosion; 2 = large erosion not passing the midline; 3 = large erosion passing the midline.

A combination of the above scores may lead to a maximum of 5 per entire joint in the hands, and 5 at each site of the joint (for the entire joint a maximum of 10) in the feet. The joint space narrowing score is based on the following features: 0 = normal; 1 = asymmetrical or minimal narrowing up to a maximum of 25%; 2 = definite narrowing with loss of up to 50% of the normal space; 3 = definite narrowing with loss of 50 to 99% of the normal space or subluxation; 4 = absence of a joint space, presumptive evidence of ankylosis, or complete luxation.

Gross osteolysis and pencil in cup are scored separately. In the final summary score, joints with 1 of these abnormalities get the maximum score assigned for both erosions and for joint space narrowing. The maximum possible scores are 320 for erosions, 208 for joint space narrowing, and 528 for the total score.

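### SAP Appendix 2.10 omits the feet from the films read centrally for the mTSS, in conflict with the protocol, which films and scores them

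*SAP*

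**What the plan says.** **SAP.** Appendix 2.10 first lists the kinds of damage that the mTSS captures. On which films are read, it says: "Hands/wrists radiographs will be obtained by sites and sent for central review". It continues: "The central reviewers will use the modified total Sharp Score (mTSS) to evaluate for radiographic damage and progression". It gives no joint list, grades, sub-scores or range, and does not refer back to the protocol's description. No other part of the SAP mentions foot films.

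**Protocol.** Section 8.1.3.8 says: "Radiographs of hands, wrists, and feet will be performed at baseline, Week 16, and Week 52 or EOT". The radiograph row of the Schedule of Activities (Section 1.3) reads "Hands, Wrists, and Feet", and its footnote i again includes the feet for subjects who stop at Week 16 or later. On scoring, Section 8.1.3.8 says of the mTSS: "It typically assesses joints of the hands and feet, including the second to fifth distal interphalangeal joints of both hands". It then gives the per-joint limits, "The maximum score for erosions is 5 in the joints of the hands and 10 in the joints of the feet", and the totals, "The maximum possible scores are 320 for erosions, 208 for joint space narrowing, and 528 for the total score".

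**Use of the score.** Change in mTSS at Weeks 16 and 52 is an exploratory endpoint (protocol Section 3; SAP 2.2.3, 2.6 and 6.6.5). The mTSS is also summarised as a baseline characteristic (SAP 6.4.2).

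**The concern.** The two documents describe different sets of films for a score with the same name. The protocol's score needs foot joints to reach its stated maximum, and the SAP's only statement about what goes to the readers leaves them out. Someone working from the SAP alone could specify or programme a hand-and-wrist score and report it as the protocol's mTSS.

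What is at stake is the meaning of the structural-progression endpoint. A hand-and-wrist score could not register change in the feet and would run on a shorter scale than the protocol states. If some totals included the feet and others did not, they would not be comparable, and Appendix 2.10 has no text that would settle which total applies.

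**Working it through.** **Inputs, all from protocol 8.1.3.8**
- Maximum erosion score: 320. Maximum joint space narrowing score: 208. Maximum total: 528.
- Erosion maximum per joint: 5 in the hands, 10 in the feet.
- Narrowing maximum per joint: 4, the top grade ("4 = absence of a joint space, presumptive evidence of ankylosis, or complete luxation").
- Number of foot joints: not stated, so it has to be derived.

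**Step 1: reproduce the stated total.** 320 + 208 = 528. This matches.

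**Step 2: joints scored for narrowing.** 208 / 4 = 52.

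**Step 3: split into hand/wrist joints (h) and foot joints (f).** Assume that the same joints are scored for erosion and narrowing, and that wrist joints take the hand limit of 5. Then:
- h + f = 52
- 5h + 10f = 320

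Subtracting 5 × 52 = 260 from 320 leaves 5f = 60, so f = 12 and h = 40. Both are whole numbers, so the assumption fits the stated maxima, though it is not proved by them.

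**Step 4: points carried by each region**

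| | Erosion | Narrowing | Total |
|---|---|---|---|
| Hands/wrists (40 joints) | 200 | 160 | 360 |
| Feet (12 joints) | 120 | 48 | 168 |
| All (52 joints) | 320 | 208 | 528 |

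Share in the feet: 120/320 = 37.5% of erosion, 48/208 = 23.1% of narrowing, and 168/528 = 31.8% of the total. A hand-and-wrist score has a maximum of 360.

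**Step 5: relax the assumption.** If the joint sets for the two parts differ, the maxima no longer fix the number of foot joints. Let the feet contribute fE joints to erosion and fN to narrowing; their share is (10·fE + 4·fN) / 528.
- fE = fN = 10: (100 + 40) / 528 = 140/528 = 26.5%
- fE = 10, fN = 14: (100 + 56) / 528 = 156/528 = 29.5%
- fE = 14, fN = 10: (140 + 40) / 528 = 180/528 = 34.1%
- fE = fN = 14: (140 + 56) / 528 = 196/528 = 37.1%

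With 10 to 14 foot joints in each part, the share runs from 26.5% to 37.1%.

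**The case against.** The strongest reply is that this is an incomplete film list in one descriptive sentence.

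- The SAP does not say that hands and wrists alone are read, and its next sentence has the readers apply the mTSS without qualification. The only working definition of that score is the protocol's, which includes the feet. The SAP sets out no hand-only version and no reduced maximum.
- The SAP names the protocol as its source (SAP 1) and defers to the protocol's schedule for assessments (SAP 2.1). A SAP appendix does not change which films sites take.
- What the readers score is fixed in a central-reading specification, which is not among the documents.
- The endpoint is exploratory. Its Week 16 p-values are descriptive, and none are reported after Week 16 (SAP 6.6.5).

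Most of this stands. A drafting slip is a plausible explanation, and the rank of the endpoint limits the consequence. It does not remove the conflict: Appendix 2.10 is where the SAP says what is read for this score, it omits a region that the protocol films and scores, and nothing elsewhere in the SAP restores it.

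A reader might go further and infer that foot progression will go unmeasured, or that subjects are exposed to foot radiographs for no purpose. The documents do not support either inference. Both would require the reading specification to follow the SAP's literal wording, and the documents do not show that it does.

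**Conclusion.** The inconsistency is real and lies in the current text of both documents. Taken literally, SAP Appendix 2.10 yields a score that is not the protocol's mTSS. The omitted region carries about 32% of the possible points (168 of 528) if the same joints are scored for erosion and narrowing, and 26.5% to 37.1% for 10 to 14 foot joints in each part.

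It would be easy to read this as a third of the information on progression being lost. It is a share of the theoretical range only. The documents give no mean or standard deviation for the mTSS, so nothing can be said about the share of expected change, of variance or of power.

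No primary, secondary or other alpha-controlled result is affected. Nor does the conflict by itself call for a rule that sets the mTSS to missing when foot films are unread. That would be a separate missing-data choice needing its own justification.

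**What to change.** In SAP Appendix 2.10:

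1. Name radiographs of the hands, wrists and feet as those sent for central reading.
2. State the 0-528 range with its erosion (320) and joint space narrowing (208) sub-scores, as in protocol 8.1.3.8.
3. Confirm that the central-reading specification covers the same films and joints.

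If a hand-and-wrist score was intended, say so in the SAP, give the reason and state the reduced maximum (360 under the joint split derived above), so that it is not reported as the protocol's score.

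The cost is a short change of wording and one check against the reading specification. The foot films are already in the schedule, so no new procedure is needed.

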**Appendix 2.11 Minimal Disease Activity (MDA) and Very Low Disease Activity (VLDA)**

A subject is classified as in MDA when 5 of the following 7 criteria are met:

- 68 tender joint count  $\leq 1$
- 66 swollen joint count  $\leq 1$
- PASI  $\leq 1$  or BSA  $\leq 3\%$
- Subject's Pain Assessment (visual analogue scale [VAS])  $\leq 15$  mm
- Subject's Global Activity VAS  $\leq 20$  mm (corresponds to Subject's Global Assessment of Disease Activity)
- HAQ-DI  $\leq 0.5$
- Tender enthesal points  $\leq 1$  site out of 6 sites included in LEI.

A subject is classified as in very low disease activity (VLDA) when all 7 criteria described above are met.

